3 STUDY DESIGN

3.1 General Design and Study Schema

The study is a prospective, open-label, multicentre, single-arm, interventional study intended to evaluate the efficacy and safety of triptorelin 3-month formulation in Chinese children with CPP.

Main study phase:

A total of 32 participants, including at least three boys, will be enrolled in the study and treated with an intramuscular (i.m.) injection of triptorelin on Day 1 of the study and at Month 3 (3 months after the first injection). Triptorelin injections do not have to be adapted based on body weight but the participant should have a minimum weight of 20 kg.

The study consists of a Screening period (the Screening visit will take place up to 28 days before enrolment), during which participants with CPP will be screened for eligibility before receiving the first triptorelin injection (Day 1 of the study) and will visit the study centre at Month 3 and Month 6 for efficacy and safety assessments (Figure 1). Participants will receive a total of two injections during the study period before they attend the End of Study (EOS) visit at Month 6.

[figure not shown]
Each participant is expected to be enrolled in this study for a minimum of 6 months and up to 7 months (including Screening period).

Participants who complete the study will perform final procedures and assessments at the final visit (Month 6). Participants who withdraw from the study before the completion of the evaluation period will be invited to attend an Early Withdrawal visit to perform early discontinuation procedures and assessments.

Details for study procedures and schedule of assessments can be found in Section 5.

Specific details regarding study treatment are provided in Section 6.

Figure 1 Main Study Design

[figure not shown]

Extension phase:

The extension of the study will provide the possibility for subjects to continue with their study drug treatment, per investigators decision, for an additional 6 months. This will imply a triptorelin injection at the Month 6 Visit and an additional triptorelin injection at Month 9, before they attend the End of Extension Phase (EOEP) visit at Month 12. This Extension phase is optional.

Each participant may be treated with the study drug for up to 12 months.

Figure 2 Extension Phase Design

EOEP = End of Extension Phase.

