- c Eligibility check of inclusion and exclusion criteria to occur at Screening and prior to dosing on Day 1. All subjects should receive brain MRI to confirm CPP and check for tumours at screening, unless they have available brain MRI scans within 6 months for site to verify.

- d PK Samples on Day 1 to be taken predose and at 4 hours post-injection (\pm 2-hour window); PK sample at Month 3 visit to be taken predose; PK sample at the Month 6 EOS/early withdrawal visit.
- e Basal LH and FSH samples to be drawn before GnRH test. Blood sampling should be taken at approximately the same time of day during each visit.
- f GnRH test samples for LH and FSH concentrations will be collected at 30, 60 and 90 minutes (\pm 5 minutes at each timepoint) after the GnRH test. The LH and FSH samples will all be taken before injection of triptorelin, if applicable (e.g. Month 3 visit).
- g Oestradiol and Testosterone samples for girls and boys, respectively.
- h Tanner pubertal stage as defined in [Appendix 1](#).
- i Auxological parameters including height, growth velocity, weight, BMI will be assessed.
- j Bone Age by Greulich and Pyle method.
- k Gonad development uterine length in girls or testicular volume in boys assessed by type B ultrasound.
- l Body weight participants should weigh \geq 20 kg on inclusion in the study.
- m Adverse events will be collected up to and including the Month 6 visit (i.e. Day 182 \pm 3 days)
- n Pregnancy test for female participants only. Girls who have entered menarche must have a negative pregnancy test prior to the start of study treatment and should not be at risk of pregnancy throughout the study period. Local urine testing will be standard for the protocol unless serum testing is required by local regulation or IRB/IEC before drug treatment for all female participants of childbearing potential and if clinically indicated thereafter.
- o Clinical laboratory tests including chemistry, haematology and urinalysis. In case of abnormal blood glucose as per Investigator's judgement, repetition of these tests will be performed before the first injection.
- p Physical examination and vital signs blood pressure and heart rate.
- q Prior and concomitant medications assessed at every visit
- r Study drug administration following all other assessments, apart from PK samples on Day 1.

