- s Local tolerability Measured by tenderness, redness, bruising, erythema, swelling, rash, pain, itching, induration, haematoma, ulceration or necrosis. To be assessed at injection and 2 hours post injection.
- t EOS/Early Withdrawal For participants who do not have a final visit within 3 months (i.e. up to Day 182 \pm 3 days) after their last triptorelin dose, efficacy evaluations (including PK sampling) will not be performed. Data from any efficacy evaluations performed after this time will not be collected on the eCRF.

Extension phase

The schedule of procedures and assessments to be performed during the extension study is summarised in [Table 2](#).

Table 2 Schedule of Assessments in Extension Phase

	Extension phase Baseline	Month 9	Month 12
	Day 1 (day 182 - Month 6)	Day 271	Day 365 (EOEP/Early Withdrawal) [h]
Study procedures [a]		±3 days	±3 days
Informed consent/assent [a]	X		
Basal LH and FSH		X	X
GnRH test with samples for LH and FSH [b]			X
Oestradiol or testosterone samples		X	X
Pubertal Stage (Tanner method)			X
Auxological parameters [c]		X	X
Bone age and chronological age [d]			X
Gonad development [e]			X
Adverse events	X	X	X
Pregnancy test			X
Clinical laboratory tests [f]		X	X
Physical examination and vital signs		X	X
Prior and concomitant medications		X	X
Study drug administration	X	X	
Local tolerability [g]	X	X	

BMI=Body mass index; eCRF=electronic case report form, EOEP=End of Extension Phase; FSH=Follicle-stimulating hormone; GnRH=Gonadotropin-releasing hormone; IEC=Independent Ethics Committee; IRB=Institutional Review Board; LH=Luteinising hormone

Footnotes to Schedule of Assessments

a Informed consent/assent to be performed by parent/legal guardian and by children if determined by local IRB/IEC requirements.

b GnRH test samples for LH and FSH concentrations will be collected at 30, 60 and 90 minutes (±5 minutes at each timepoint) after the GnRH test. The LH and FSH samples will all be taken before injection of triptorelin, if applicable.

c Auxological parameters including height, growth velocity, weight, BMI will be assessed.

d Bone Age by Greulich and Pyle method.

e Gonad development uterine length in girls or testicular volume in boys assessed by type B ultrasound.

f Clinical laboratory tests including chemistry, haematology and urinalysis.

g Local tolerability Measured by tenderness, redness, bruising, erythema, swelling, rash, pain, itching, induration, haematoma, ulceration or necrosis to be assessed at injection.

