5.2.2 Procedures During the Treatment Phase of Study (Day 1 and Month 3)

The participant's eligibility for the study will be checked again at Day 1 visit (based on the Inclusion and Exclusion criteria presented in Section 4.1 and 4.2, respectively) before the other assessments listed in [Table 1](#).

Participants will be admitted at the clinical site on the morning of Day 1 and the Month 3 visit and the assessments described in [Table 1](#) will be performed. Study drug administration will follow after the other assessments, apart from any post-dose PK samples and local tolerability.

5.2.3 Procedures Following Study Treatment (Month 6, End of Main Study or Early Withdrawal Visit)

Participants who complete the main study will perform final procedures and assessments at the final visit (Month 6). Participants who withdraw from the study before the completion of the evaluation period will be invited to attend an Early Withdrawal visit to perform early discontinuation procedures and assessments (as in [Table 1](#)).

For participants who do not have a final visit within 3 months (i.e. up to Day 182±3 days as in [Table 1](#)) after their last triptorelin dose, efficacy evaluations should not be performed. Data from any efficacy evaluations performed after this time will not be collected on the eCRF.

Participants with ongoing AEs or clinically significant laboratory test abnormalities (as determined by the Investigator) will be monitored as described in Section 8.1.4 and Section 8.1.2.4, respectively. The AEs will be collected up to 3 months after the date of the last injection.

5.2.4 Procedures During the Extension Phase (Month 6, Month 9 and End of Extension Phase Visit)

At the end of the main study, participants who are still benefiting from treatment (i.e. not progressing) and who have not experienced any unacceptable safety issues, will have the option to continue to receive triptorelin every 3 months in the 6-month extension phase.

The participant's eligibility for the extension phase will be checked at Extension Phase Day 1 visit (Month 6) (based on the Inclusion criteria presented in Section 4.3, respectively). The Extension Phase Day 1 visit will correspond to the End of main Study Visit.

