Participants will be admitted at the clinical site on the morning of Month 6, Month 9 and Month 12 visit and the assessments described in [Table 2](#) will be performed. Study drug administration will follow after the other assessments on the Month 6 and Month 9 visits, apart from any post-dose PK samples and local tolerability.

For participants who do not have a final visit within 3 months (i.e. up to Day 365±3 days as in [Table 2](#)) after their last triptorelin dose, efficacy evaluations should not be performed. Data from any efficacy evaluations performed after this time will not be collected on the eCRF.

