### 5.8.3 *Adverse Event*

All adverse events (AEs) recorded in the eCRF will be coded using the latest version of MedDRA dictionary in effect within IPSEN at the time of the database lock. AEs will be classified as treatment-emergent AEs (TEAEs) according to the rules below:

- Events with start date on or after the date of first IMP administration and up to the EOS or 185 days after first dose days which comes first.
- Events whose CTCAE grade worsens on or after the date of first IMP administration,
- Events whose causality changes to “Related” on or after the date of first IMP administration,
- Refer to appendix [Partial/Missing Date Convention A2](#) for handling of partial date. In the case where it is not possible to define an AE as treatment emergent or not, the AE will be classified by the worst case; i.e. treatment emergent.

Tabular summaries will be presented by gender. Summaries will include the number and percentage of participants and classified by primary system organ class and preferred term. The following summaries will be reported for AEs, TEAE regardless of drug relationship, TEAE related to study drug, TEAE grade 3 and above regardless of drug relationship, TEAE grade 3 and above related to study drug, serious AEs (SAEs), AE leading to study drug discontinuation, and AE leading to death:

- An overview table summarizing the number and percentage of participants with at least one of the following AEs: any AE; any TEAE; SAE, treatment emergent SAE, treatment-related TEAE, treatment emergent-related SAE, Non-serious TEAEs, TEAE leading to treatment discontinuation; TEAE leading to discontinuation from the study, CTCAE Grade  $\geq 3$  TEAE, Death, TEAE leading to death,
- A summary of the number and percentage of participants reporting a TEAE by gender, SOC and PT,
- A summary of the number and percentage of participants reporting a SAE by gender group and PT,
- A summary of the number and percentage of participants reporting a Serious TEAE by gender group and PT,
- A summary of the number and percentage of participants reporting a treatment-related Serious TEAE by gender group and PT,
- A summary of the number and percentage of participants reporting a TEAE leading to treatment discontinuation by gender group and PT,
- A summary of non-serious TEAE by gender group, SOC and PT,
- A summary of TEAE by gender group and PT,
- A summary of the number and percentage of participants reporting a TEAE by gender group, CTCAE grade, SOC and PT,

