- A summary of the number and percentage of participants reporting a drug-related TEAE by gender group, CTCAE grade, SOC and PT,
- A summary of the number and percentage of participants reporting a TEAE by gender group, causality, SOC and PT,
- A summary of most frequent AEs (reported in  $> 5\%$ ) by gender group, SOC and PT.

AEs summaries will be ordered in term of decreasing frequency for SOC and PT within SOC in the gender, and then alphabetically for SOC and PT within SOC.

AEs will be counted as follows:

- Participants with more than one AE within a particular SOC are counted only once for that SOC. Similarly, participants with more than one AE within a particular PT are counted only once for that PT;
- Participants reporting a TEAE more than once within that SOC/ PT, the TEAE with the worst case CTCAE grade will be used in the corresponding CTCAE grade summaries;
- Participants reporting a TEAE more than once within that SOC/ PT, the TEAE with the worst case relationship to study medication will be used in the corresponding relationship summaries;
- If the CTCAE grade is missing for a TEAE, it will be considered as missing in the summary tables;
- If the causality is missing for a TEAE, it will be considered related in the summary tables;
- The non-serious TEAEs table should include a specific row “any non-serious TEAE above 10%;
- A TEAE is counted only in the study where it started (if there is a change in the CTCAE grade an additional AE should have been collected in the eCRF).

In addition, a listing with all AEs data will be listed by gender group including non-TEAEs, Treatment-emergence status will be flagged in the listing. Listing of Drug-related AEs will also be added.

The following listing will also be provided:

- A listing of all deaths that occurred during the study,
- A listing of all serious adverse events,
- A listing of all adverse events leading to discontinuation of study treatment.

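### The SAP's date rule can count same-day reactions to the Month 6 injection in the main phase and leave them out of the extension

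*SAP*

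**What the plan says.** SAP 5.8.3 sets the only TEAE window in the plan: "Events with start date on or after the date of first IMP administration and up to the EOS", with a cap given in the same line ("up to the EOS or 185 days after first dose days which comes first"). The counting rules in that section add that "A TEAE is counted only in the study where it started". For the extension, SAP 5.9.2 says only that adverse events are analysed as in the main phase; it gives no start, no end and no rule for a shared date.

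The shared date comes from the protocol. Section 5.2.4 says "The Extension Phase Day 1 visit will correspond to the End of main Study Visit", and Table 2 labels the extension baseline column "Day 1 (day 182 - Month 6". Section 3.1 places the third injection there: "This will imply a triptorelin injection at the Month 6 Visit and an additional triptorelin injection at Month 9". On order within the visit, section 5.2.4 says "Study drug administration will follow after the other assessments on the Month 6 and Month 9 visits", with post-dose samples and local tolerability excepted. Section 8.4 has the site examined at injection and 2 hours later; Table 2 footnote g names the check at injection. Either way it falls on the injection date.

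On collection, Table 1 footnote m says "Adverse events will be collected up to and including the Month 6 visit". For local reactions reported as adverse events, protocol 8.1.2.6 names start and stop dates but no onset time.

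**The concern.** A date rule cannot separate what happened before the third injection from what happened after it on the same day. The main phase is described throughout as two injections, yet its TEAE window includes the day of a third for every child who continues. The extension also has two injections, and it could lose the same-day reactions to one of them.

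TEAE incidence including local tolerability is a safety endpoint in both phases, and the phases are analysed separately. If the literal reading is programmed, the main phase looks less well tolerated than two injections would make it. The extension, which is meant to describe longer-term safety, looks better tolerated than it was.

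**Working it through.** **Step 1: which limit ends the main-phase window.** Table 1 puts Month 6 at Day 182 ± 3, so Day 179 to Day 185. The plan's own figure of 185 matches the upper edge: 182 + 3 = 185. SAP 5.1.4 counts the first dose as Day 1, so EOS on Day 179, 182 or 185 is 178, 181 or 184 days after the first dose. A cap of 185 days after the first dose is Day 186. An EOS visit within its window therefore always comes first and ends the window. (If the visit slips past Day 186, the cap comes first and a same-day reaction falls outside the main window.)

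**Step 2: which reactions are caught.** Let the lag be onset date minus EOS date, for an in-window EOS.

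- Lag 0: onset is on the EOS date, which SAP 5.8.3 does not exclude. Inside the main-phase window.
- Lag 1 day or more: onset is after EOS. Outside.

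So only same-day onsets are affected, and only in children who receive the Month 6 injection.

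**Step 3: what happens in the extension.** Once an event is assigned to the main phase, the one-phase rule leaves no place for it in the extension. The main-phase window cannot simply be copied across, because it would end at EOS or 185 days and exclude new events later in the extension. The extension needs its own window, and the SAP does not give one.

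**Step 4: illustration of size.** Planned injections with all 32 continuing: 32 × 2 = 64 in each phase. Under the literal rule, same-day reactions from 32 × 3 = 96 injections fall in the main phase and from 32 × 1 = 32 in the extension.

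Assume a same-day reaction risk p per injection, independent between injections. The documents give no value, so p is varied from 2% to 20%. The proportion of children with at least one reaction over k injections is 1 − (1 − p)^k. At p = 10%: 1 − 0.9³ = 27.1%, 1 − 0.9² = 19.0%, and 10.0% for a single injection.

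| p | Main, literal (k = 3) | Main, by injection (k = 2) | Extension, literal (k = 1) | Extension, by injection (k = 2) | Main, literal, 16 of 32 continue |
|---|---|---|---|---|---|
| 2% | 5.9% | 4.0% | 2.0% | 4.0% | 4.9% |
| 5% | 14.3% | 9.8% | 5.0% | 9.8% | 12.0% |
| 10% | 27.1% | 19.0% | 10.0% | 19.0% | 23.05% |
| 20% | 48.8% | 36.0% | 20.0% | 36.0% | 42.4% |

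The last column is half the k = 3 value plus half the k = 2 value; at 10%, (27.1 + 19.0)/2 = 23.05. The extension columns refer to children who enter the extension.

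**Step 5: clustering.** If reactions cluster within children, the gap in children with at least one reaction shrinks. If the same 10% of children react to every injection and the rest to none, the proportion is 10% for any k, and the gap is zero. The number of events assigned to each phase would still shift.

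**The case against.** The strongest reply is that the plan leaves a tie and does not direct these events to either phase. No sentence says that reactions to the Month 6 injection belong to the main phase or are barred from the extension. The counting rule speaks of the study in which an event started, and a reaction to the extension's first injection can fairly be read as starting in the extension. Table 1 has no injection or local tolerability check at Month 6; Table 2 has both. If SAP 5.9.2 is adapted sensibly, an extension window would open at the Month 6 injection, and the event would fit both windows.

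This stands as far as it goes. A reader might infer that the SAP expressly excludes these reactions from the extension; the documents do not support that. Exclusion follows only from a literal reading of the window together with the one-phase rule. But the one window that is written is a date rule that reaches the EOS date, and the schedule points the other way. Nothing resolves the two.

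Three further limits also stand. Only local reactions judged clinically significant become adverse events (protocol 8.1.2.6 and 8.4), and the separate local tolerability summary in the SAP states no phase rule at all. The study is descriptive, with no hypothesis test. All adverse events and local reactions are listed with dates and study days, so a careful reader could find the Month 6 reactions. The listings reduce the harm but do not correct the summary tables.

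**Conclusion.** The point holds in a limited form. Taken literally, SAP 5.8.3 counts same-day reactions to the third injection in the two-injection main phase, and they may then be missing from the extension, where protocol Table 2 places that injection. The direction on that reading is main phase up, extension down.

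It would go too far to say that all reactions to the Month 6 injection are misplaced, or that the tolerability results of either phase will be distorted by a known amount. Later-onset reactions are outside the main window, children who stop at Month 6 are unaffected, and the percentages rest on assumed rates, independence and extension uptake. The 8.1-point excess in the main phase (27.1% − 19.0%) and the 9.0-point shortfall in the extension (19.0% − 10.0%) apply only to a 10% independent risk with all 32 continuing. With 16 continuing, the main-phase excess is about 4 points (23.05% − 19.0%); with complete clustering it is zero.

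The primary endpoint is not touched. The rule should still be settled, because it decides which phase reports the immediate reactions to one of the extension's two injections.

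**What to change.** In SAP 5.8.3, in the local tolerability summary and in SAP 5.9.2, state that for children who receive the Month 6 injection the main-phase window ends immediately before that injection and the extension window starts at it. Use the dose date and time, which protocol 6.5 already requires to be recorded. For other children the main-phase window stays as it is.

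Add a default for events on that date with no onset time: assign injection-site reactions to the extension, and keep findings from the pre-injection Month 6 assessments in the main phase. Sending every untimed same-day event to the extension would create the opposite error, because laboratory tests and the physical examination at that visit precede the injection.

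The cost is SAP wording, one extra derivation and possibly an onset-time field for adverse events on dosing days. No visit or procedure is added. Tabulating local tolerability by injection number (1 to 4) would make the attribution visible, but is optional.

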A TEAE is defined as any AE that occurs during the active phase of the study (between the start date of the treatment and the end of study treatment) if:

- It was not present prior to receiving the first dose of triptorelin, or
- It was present prior to receiving the first dose of triptorelin but the grade increased or became serious during the active phase of the study, or
- It was present prior to receiving the first dose of triptorelin, the grade/seriousness is the same but the causality changed to “related” during the active phase of the study.

All TEAEs will be flagged in the AE listings.

Summary incidence tables will be provided, classified by SOC, PT and associated NCI-CTCAE worst grade. In the event of multiple occurrences of the same AEs being reported for the same participant, the maximum intensity (Grade 5 > Grade 4 > Grade 3 > Grade 2 > Grade 1 > missing > not applicable) will be chosen. All AEs will be collected up to the EOS visit (see [Table 1](#) for schedule), or EOEP visit for those enrolled in the extension phase.

Concomitant medication will be coded by using World Health Organization Drug Dictionary (WHO-DD) version (current version in use at the start of the study) and will be summarised with the number and percentage of participants receiving concomitant medication by drug class and preferred drug name.

Haematological and biochemical toxicities will be recorded and graded according to the NCI-CTCAE criteria, where available. The NCI-CTCAE Grades 3 and 4 haematology and biochemistry variables will be listed by participant and by visit.

Actual values and changes from Baseline in clinical laboratory tests, physical examinations and vital signs will be summarised using descriptive statistics at each visit. For laboratory data, abnormal values will be flagged in the data listings and a list of clinically significant abnormal values will be presented. Shift tables using the worst on-treatment grade will be presented for the number and percentage of participants with NCI-CTCAE grades.

11.4.7 *Efficacy and Safety Evaluations (Extension Phase)*

A separate analysis on efficacy and safety endpoints will be performed considering the extension phase duration, a period of an additional 6 months, lasting until the End of Extension Phase Visit at Month 12.

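### As written, the SAP's adverse-event rules can flag a pre-dose event that only improves after dosing as treatment-emergent, which Protocol 11.4.6 does not allow; the effect is small

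*SAP*

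**What the plan says.** SAP 5.8.3 gives three routes to TEAE status. The first is by date: "Events with start date on or after the date of first IMP administration and up to the EOS or 185 days" after first dose, whichever comes first. The second is by grade: "Events whose CTCAE grade worsens on or after the date of first IMP administration". The third is a change of causality to related. They are listed as parallel routes, and none limits another.

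The same section, under its counting rules, says: "A TEAE is counted only in the study where it started". A parenthesis attached to that sentence adds: "if there is a change in the CTCAE grade an additional AE should have been collected in the eCRF". The parenthesis speaks of a change, with no direction given.

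Protocol 11.4.6 is narrower. An event counts if it was absent before the first dose. An event already present counts only if it meets a further condition: "but the grade increased or became serious during the active phase of the study", or its causality became related during that phase. SAP 2.6 states that the SAP makes no change to the protocol's statistical section.

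**The concern.** The date rule and the record-splitting remark are each unremarkable alone. Together they may bypass the protocol's direction test. If every grade change produces a record with its own start date, a record created because a child got better starts after first dose, and the date rule accepts it. The grade rule, which looks only for worsening, is never consulted.

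Recovery from an illness that predates treatment would then appear as a treatment-emergent event. The TEAE flag feeds most of the adverse-event tables in SAP 5.8.3, and all of them are shown for girls, boys and overall (SAP 5.1.1.1), so the boys' column is very small. The reported incidence would follow a definition other than the protocol's, with no departure declared.

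**Working it through.** The plan gives no figure to reproduce. The check applies both sets of rules to one case and then sizes one misclassified child.

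**Can the case arise?** Protocol 8.1 collects adverse events from informed consent, and screening runs from Day -28 to Day -1, so an event can be ongoing at first dose.

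**Test case.** Grade 2 event with onset on Day -10, easing to grade 1 on Day 15; not serious, causality unchanged.

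| Rule set | Condition tested | TEAE? |
|---|---|---|
| SAP, additional record dated Day 15 | Start between Day 1 and Day 185: yes | Yes, by the date rule |
| SAP, original onset of Day -10 kept | Date: no. Grade worsened: no. Causality changed: no | No |
| Protocol 11.4.6 | Absent before dosing: no. Grade increased: no. Became serious: no. Causality changed: no | No |

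If the same event worsens on Day 15 instead, both documents call it a TEAE. For grade changes, the disagreement is confined to improvement.

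**The step that is inferred.** The result depends on the start date of the additional record, which the SAP does not give. The parenthesis explains how an event is assigned to the study in which it started, and it helps with that only if the additional record has its own start date. That supports the reading. The eCRF completion rules are not in the documents, so it remains an inference. Where status cannot be determined, the SAP's default also leans towards flagging: "the AE will be classified by the worst case; i.e. treatment emergent".

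**Size of one misclassified child.** Inputs: 32 planned participants including three boys (SAP 2.2), hence 32 - 3 = 29 girls if exactly three boys enrol. The safety population is assumed equal to planned enrolment. The child must have no other TEAE, overall or under the preferred term in question.

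- Overall: 1/32 = 3.1 points
- Girls: 1/29 = 3.4 points
- Boys: 1/3 = 33.3 points

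The boys' figure reflects a column of three rather than a large effect. Two such children give 2/32 = 6.25 points. Under a single preferred term, that would pass the cut-off of more than 5% in the SAP's table of most frequent events, if that table counts only TEAEs. Its title refers to AEs, so this is uncertain.

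**The case against.** The strongest reply is that only worsening was meant. The grade rule names worsening explicitly. If every grade change created a newly dated record, that rule would be largely redundant within the main phase. It has a natural role only if a pre-dose event keeps its onset date. Protocol 8.1.1 points the same way: it describes adverse events as new or exacerbated conditions and excludes anticipated fluctuations of pre-existing conditions that do not worsen. Protocol 8.1.4 has continuing events reviewed at later visits and does not ask for a new entry when they ease. The parenthesis also qualifies a sentence about events that are already TEAEs, not about pre-dose events.

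This is good evidence of intent, and it stands as such. But the grade rule is a separate route and does not narrow the date rule. Nor do the protocol's definitions say how a record already opened for a grade change should be dated or flagged. A programmer following SAP 5.8.3 literally, given a record that starts on Day 15, would flag it.

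Two further replies limit the effect. Under the counting rules, "participants with more than one AE within a particular PT are counted only once for that PT", so repeats within a term do not inflate incidence; a child whose only treatment-emergent record under that term is the improvement still enters the count. And all events are listed with their TEAE status, so a wrong flag can be seen in the listing, though not in the tables.

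**Conclusion.** There is a small main-phase mismatch between SAP 5.8.3 and Protocol 11.4.6. On the SAP's wording, a pre-dose event that only improves can be flagged as treatment-emergent, provided the additional record is dated at the grade change. Each affected child adds 3.1 points overall at the planned 32. The documents give no basis for predicting how many there will be. It takes an event of grade 2 or higher ongoing at first dose that then steps down and is recorded separately, so the number may well be zero.

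A reader might also infer that a main-phase event easing after Month 6 is counted a second time as a new extension TEAE. The documents do not support that. The date rule closes at the end-of-study visit or 185 days, easing satisfies neither of the other two routes, and SAP 5.9.2 carries the main-phase analysis over without stating an extension window. Nor can it be said that TEAE incidence will be inflated to any material degree. The point is a clarification worth making because the flag is used so widely and the remedy is so cheap.

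**What to change.** In SAP 5.8.3:

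1. Restrict the date rule to events not present before the first dose.
2. State that a record opened because the grade of an ongoing pre-dose event decreased keeps the original onset date for the TEAE flag.
3. State that such an event becomes treatment-emergent only if its grade increases, it becomes serious, or its causality changes to related, as in Protocol 11.4.6. Becoming serious is not among the SAP's listed routes at present, so this also completes the alignment.

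The cost is a sentence or two of SAP text and a variable linking each continuation record to its parent event in the adverse-event dataset. The linking takes some data-review effort, but it needs no new assessments and no change to how children are managed.
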